2.5 Study Procedures

	
which may decrease the incidence of residual neuromuscular block.)
 
 1) The ExSpirom will be placed on the patients' chest prior to extubation. ExSpirom data will be collected starting prior to tracheal extubation, during transport from OR to PACU, and in PACU. 2) Patient care staff will be blinded to the ExSpirom numerical and trending data for MV, TV and RR, but the respiratory trace will be displayed to demonstrate that the ExSpirom is functioning. Of note, the gain on the trace is variable so the size of the breath visualized on the screen is not correlated to the volume of the breath. This will maintain blinding of the patient care staff. 3) TOF Monitoring with an objective monitor (TOF-Watch or StimPod) will be used in all patients once the decision to extubate the patients' trachea is made. The monitoring will continue in the PACU until full recovery (TOF=1.0) is documented. Monitoring will be performed as per usual clinical routine via surface ECG electrodes. In the PACU, the current amplitude will be decreased to 30-40 mA, current intensities that are used routinely for patient care in other centers and that do not result in patient discomfort. 4) Patient care staff will be blinded to TOF data. Only the investigator assigned to the PACU data retrieval will know the results of TOF Monitoring. 5) Patient care should follow standard hospital protocol. 6) Physiologic monitoring and clinical assessment data will be recorded as per standard protocol in the PACU. 7) All other therapies and medications including oxygen, CPAP, opioids and sedatives will be delivered in accordance with standard of care. 8) Doses and times of all medications (such as opioids, sedatives, etc.) or respiratory interventions (such as albuterol, respiratory treatment, suctioning, high flow oxygen, CPAP, BiPAP, etc.) will be recorded throughout the entire perioperative period (pre-op, OR, PACU). 9) Pain scores based on a standard analog scale (1-10) will be recorded. These will be obtained per standard clinical practice. 10) Arterial or venous blood gas values and Chest x-rays taken in the OR or PACU will be recorded when obtained as part of standard care. 
B. Study Procedures
 
 1) Screening and Recruitment: Study personnel will review the surgery schedule to identify appropriate and eligible patients. Eligible
--	--

	
patients will be informed about the study and the study will be explained to them. They will be able to ask questions. If they would like to participate, written informed consent will be obtained. Recruitment at Mayo Clinic site will be conducted by Investigators on the day of surgery. Patients will be identified and approached before they are taken to the preoperative area. A private room located near the surgical area will be used for consenting of prospective participants. Family and/or friends will be allowed to remain with a patient during the consenting process. Patients usually arrive approximately 2 hours prior to their scheduled surgery time, which will be adequate time to discuss the study and allow patients to make an informed decision whether or not to participate in this research study.
 
2) Randomization:
 
Patients will be randomized to one of two groups: administration of sugammadex (n=150) vs. placebo (n=150) prior to tracheal extubation in the OR.
 
3) Prior to Procedure (in the OR or preoperative area):
 
 i. For RVM monitoring, ExSpiron PadSet will be placed on the patient's thorax (see Appendix A for placement instructions). Deviations from standard placement will be documented. Once in the OR the ExSpiron will be connected and the ExSpiron will be synchronized to the ventilator. ii. For TOF monitoring, skin ECG electrodes will be placed along the ulnar nerve on the volar forearm, as per routine clinical protocol. Visual or tactile intraoperative monitoring of neuromuscular block level will be performed according to the clinicians' usual routine. At the end of surgery, once the clinician has determined that recovery of neuromuscular block is adequate (after administration of standard of care reversal agents) for maintenance of spontaneous ventilation, the TOF will be determined objectively (it will be measured with the currently available monitor, TOF-Watch or StimPod), and then the patient's trachea will be extubated, as per usual clinical routine. In 150 of the 300 patients, a dose of sugammadex (2 mg/kg) will be administered, and then routine TOF measurements will be made in the PACU. 
4) Operating Room (OR):
 
 a. Record all medications (dose, route, time)
--	--

- b. Record surgery start and end times
- c. Record position changes
- d. Record intubation and extubation times

5) Recovery Room (PACU):

- a. Record PACU arrival and check device function.
- b. Record all medications (dose, route, time)
- c. Record form and dose of administered oxygen & all changes in administered oxygen or respiratory treatments of any kind
- d. Record PACU discharge time
- e. MV, TV & RR numerical data will be hidden and not

	
available for patient care decisions, but the continuous respiratory trace will be displayed. Patient care providers should not use this trace for clinical decision-making. If the trace is absent or grossly abnormal, this should be recorded and study staff notified to ensure proper device function.
 
f. TOF data will be hidden and not available for patient care decisions
 
6) Final Discharge Parameters: Record the patients' final discharge date and time (LOS) from the PACU.
 
7) De-identification: All study data will be de-identified and identifying information will be linked to a code only accessible to the study staff. The code will be destroyed following final data analysis.
 
8) Assessment of Subject Safety and Data Safety Monitoring Plan: All patients will be followed by one of the study investigators to ensure there are no complications associated with sugammadex administration (flushing, tachycardia, hypotension, etc). There are no expected complications of RVM monitoring. There are no expected complications associated with TOF monitoring, and in fact, such monitoring has been shown to improve patient safety by decreasing postoperative CREs and other complications.^{11,12} External monitoring will not be provided; however, Principal Investigator will review all data for accuracy to ensure adherence to the approved protocol. Data will be recorded by the study coordinator and all electronic study-related files will be stored on a secured Mayo Clinic server. Drug accountability and dispensing will be handled by pharmacy. Any potential adverse events will be assessed by the principal investigator for severity and relevance to the study drug.
 
9) Subject Participation:
 
 Recruitment: Subjects will be recruited in the pre-procedure holding areas by the study team members prior to their surgery. Screening Interview: Subject screening will be based on study personnel examining the surgery schedule of the next or same day to identify appropriate procedures scheduled and patient's eligibility. Informed consent process and timing of obtaining of consent: Informed consent will be obtained by the study staff prior to surgery in the preoperative holding area, in patients requiring surgery and
--	---

general anesthesia and planned extubation in the OR. After a thorough review of the study. Sufficient time will be given to the patients, parents, guardians or legal representative to ask questions and decide on participation.

- d. Location where study will be performed: University

	
of Texas, UTHealth at Houston and Mayo Clinic, Jacksonville, Florida operating holding areas, operating and recovery rooms, and intensive care units as applicable.
 
e. Personnel who will conduct the study include PI and research team members.
 
10) Subject fees: There are no fees for this study.
 
11) Procedures to protect subject confidentiality: A unique study ID number will be assigned to each subject as a means to de-identify the study data. A code will be kept separately with the PI. Study files will be kept in a locked office in a locked cabinet or a password-protected computer with encrypted study files. The location will be the PI office with restricted access. The code will be locked separately from study files in the PI office.
 
a. Certificate of Confidentiality: N/Ab. How data will be coded, recorded, and stored to protect confidentiality: All data will be de-identified. All data will be linked to the subject study ID by a code.c. Data will be analyzed by institutional biostatisticians at UTHealth at Houston.d. Parties who will have access to the data, including the key to the identity code: only [name] and J. [name] and primary study staff will have access to the master study log/key. Other investigators and the clinical and engineering staff at Respiratory Motion, Inc. will only have access to de-identified data.e. Parties who will have access to research records: Investigators on the study, Respiratory Motion, Inc. will have access only to de-identified records.f. Collaboration: This study is performed in collaboration with Respiratory Motion, Inc.g. Alternatives: The alternative to participating in this study is not participating.h. How new information will be conveyed to the study subject and how it will be documented: Other than the initial explanation of the purpose and plan for the study, we don't expect new information to
--	---

	
become available from the study that could affect a subject's willingness to participate. No new information of clinical relevance to the subject is expected from this study. Therefore no new information will be given to the patient.
 
 i. Payment: The participants will not be compensated for their participation in the study. j. Payment for a research-related injury: This is a minimal risk study. There are no plans to provide other compensation. If a participant is injured during this study, the study doctor will discuss the available medical treatment options with the subject. 
12) Outcome: The primary outcome of this study is evaluation of the effects of sugammadex on the incidence of respiration complications postoperatively.

2.6 Study Duration	We anticipate that we will recruit the planned number of patients (n=300) at the two centers (UTHealth and Mayo Clinic) within 6 months of IRB approval and receipt of all necessary study materials and medications.

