2.1 Objectives & Hypotheses

Hypotheses:

- A. After routine care and reversal of neuromuscular block as per usual clinical routine, and after tracheal extubation, surgical patients randomized to receive sugammadex vs. placebo in the OR will:
 - 1) have a lower incidence of "Decreased MV" [MV <80% MV predicted (MV_{PRED}) based on BSA] as well as lower average MV sustained at 15-30 minutes after PACU arrival than placebo patients
 - 2) have a lower incidence of "Low MV" as well as lower average MV at PACU discharge. An instance of "low MV" occurs when the measured MV is <40% MV predicted (MVPRED) based on BSA, for any contiguous 10 minutes in the 30 minutes leading up to PACU discharge.
- B. A smaller fraction of patients in the sugammadex group than in the placebo group spend more than 2 minutes in the PACU with a sustained "Low MV."
- C. A smaller fraction of patients in the sugammadex group than in the placebo group spend more than 2 minutes in the PACU with a sustained "Low MV" when corrected for PACU length-of-stay (LOS).
- D. The average %MV predicted is greater in the sugammadex group than in the placebo group.
- E. PACU LOS is shorter in patients receiving sugammadex as compared with placebo patients.
- F. Fewer patients in the sugammadex group have respiratory complications or require respiratory monitoring (O₂ desaturation, atelectasis, O₂ administration, CPAP, BiPAP, reversal medication).

	
 G. The sugammadex group has higher train-of-four (TOF) ratios than the placebo group at equivalent time points throughout their PACU stay. H. The ExSpiron is able to identify respiratory depression (defined as instances of MV <40% MV_{PRED} lasting at least 1 minute) occur prior to instances of SpO₂ <90% lasting at least 2 minutes). I. Lower MV measurements (corrected for total morphine equivalents administered) are correlated with lower TOF ratios.
--	--

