2.3 Study Design	Research Plan A. Experimental Design: Randomized Controlled Blinded Trial B. Sample size and statistical analysis: (See Section 2.7 below) C. Subject Criteria: 1) Inclusion Criteria: Patients undergoing surgery with general anesthesia Patients scheduled to receive rocuronium or vecuronium for neuromuscular blockade Patients weighing \geq 80 pounds Non-intubated patients prior to surgery Patients who are able to give informed consent. 2) Exclusion criteria: Patients unable to give informed consent. Patients scheduled to receive nonsteroidal neuromuscular blocking agents (succinylcholine or benzylisoquinolinium) Patients scheduled to receive steroid neuromuscular blocking agents other than rocuronium or vecuronium. Any patient whose condition will not allow for placement of the electrode PadSet. Patients whose tracheas were not extubated in OR or PACU. Pregnant women. Patients with known severe renal impairment (estimated creatinine clearance $<$ 30 mL/min) as documented in the medical record. Patients with known hypersensitivity to sugammadex or any of its components. 3) Withdrawal/Termination Criteria: Participants may withdraw from the study at any time for any reason, Investigators may terminate the study if this is determined to be in the best interest of the subject.
------------------	---

D. Risk/Benefit Assessment:

Sugammadex. Sugammadex has been FDA approved for clinical use in the US and it has been used worldwide since 2008. We plan to administer the smallest dose of sugammadex recommended for shallow neuromuscular block (2 mg/kg of actual body weight), a dose that has not been reported to cause allergic or any other side effects. The use of sugammadex may lead to complete reversal of residual neuromuscular block, and avoidance of the respiratory complications (CREs) associated with incomplete reversal after neostigmine.

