300 patients undergoing surgical procedures requiring general anesthesia with mechanical ventilation will be recruited and consent will be obtained. The subjects will be randomized preoperatively to receive in the OR following the procedure and prior to extubation either sugammadex (Group 1, n=150 patients) or placebo (Group 2, n=150 patients). In all patients, intraoperative surgical and anesthetic management will follow the usual clinical routine at the two enrolling institutions. Once surgery is finished, emergence from anesthesia will occur as per usual clinical routine until the clinician determines that the patient is ready for tracheal extubation. Once the decision to extubate the trachea is made, the patient will receive intravenously either sugammadex 2 mg/kg or placebo in a blinded manner. The patient's trachea will be then extubated, and postoperative anesthetic care will proceed as per usual routine. Patients will then be transferred to the PACU for postoperative care and recovery. (This methodology will ensure that all 300 patients will receive at least the current standard of clinical care. Of the 300 patients, 50% of them (n=150 patients) may benefit from the administration of sugammadex,

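### The usual-care reversal agent is not named, so a placebo patient can receive non-study sugammadex within protocol, which dilutes the comparison toward no effect

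*Combined protocol and SAP*

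**What the plan says.** Background reversal is left to local practice in three places.

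- Hypothesis A in section 2.1 sets the scene: "After routine care and reversal of neuromuscular block as per usual clinical routine, and after tracheal extubation".
- Section 2.5 A states: "In all patients, intraoperative surgical and anesthetic management will follow the usual clinical routine at the two enrolling institutions".
- Section 2.5 B.3.ii places the objective train-of-four measurement at the point "once the clinician has determined that recovery of neuromuscular block is adequate (after administration of standard of care reversal agents").

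None of these names the agent. After the study dose, section 2.5 A says that "postoperative anesthetic care will proceed as per usual routine", and item 7 there adds: "All other therapies and medications including oxygen, CPAP, opioids and sedatives will be delivered in accordance with standard of care".

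Section 2.3 D says of the test drug: "Sugammadex has been FDA approved for clinical use in the US and it has been used worldwide since 2008". The exclusions in 2.3 C.2 cover other blocking agents and known hypersensitivity to sugammadex. They do not cover planned or actual open-label sugammadex, and there is no list of prohibited medication.

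Other text points to a background without sugammadex. Section 2.3 D sets the expected benefit against incomplete reversal with neostigmine. Section 2.8 has the institutions supply the drugs for care apart from sugammadex, which is requested from the company for the 150 patients in that arm. Section 2.5 B.3.ii speaks of a sugammadex dose in 150 of the 300.

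Section 2.5 (A item 8, B.4a and B.5b) already requires every medication to be recorded with dose and time. Section 2.7 does not say how a patient given non-study sugammadex is analysed.

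**The concern.** The title and primary objective present a comparison of sugammadex with placebo. The sample size in 2.7 D assumes that the arms differ by the full effect of the drug. If usual care can itself include sugammadex, the placebo arm becomes a mixture of patients with and without the test drug, and the proportions may differ between the two sites. The observed difference then understates the effect of sugammadex against a background without it.

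Under 2.7 C, A1 must succeed before A2 is tested, and both must succeed before any other hypothesis is tested. Lost power on A1 or A2 therefore carries through the whole sequence.

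**Working it through.** **Inputs from section 2.7**

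- A1 (minute ventilation below 80% of predicted after PACU arrival): placebo 33%, reduction 0.18, so 15% on sugammadex; z values 1.96 and 0.84.
- A2 (below 40% of predicted before discharge): placebo 22%, reduction 0.11, so 11% on sugammadex; z values 1.645 (single-sided) and 0.84.
- 150 patients per arm; Fisher's exact test.

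**Assumed, not in the documents:** c, the share of the placebo arm given non-study sugammadex.

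**Step 1: reproduce the plan's figures.** With n = 2·p̄(1 − p̄)(Zβ + Zα)²/(Δp)²:

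- A1: p̄ = 0.24, so 2 × 0.24 × 0.76 × 2.80² / 0.18² = 88.27. The plan gives 88.3.
- A2: p̄ = 0.165, so 2 × 0.165 × 0.835 × 2.485² / 0.11² = 140.6. The plan gives 143.2, a gap of 1.8% that does not affect this point.

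Neither calculation allows for non-study sugammadex in the placebo arm.

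**Step 2: dilute the placebo rate.** If affected placebo patients take the sugammadex-arm rate, the placebo rate is p₁ − c(p₁ − p₂) and the difference is (1 − c)(p₁ − p₂). For A1 at c = 20%, this is 0.33 − 0.20 × 0.18 = 0.294, and the difference falls from 18 to 14.4 points. The sugammadex arm is left unchanged, meaning that a second exposure adds nothing.

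**Step 3: power.** For each pair of event counts out of 150, the binomial probabilities under the two rates were multiplied and summed over the pairs with Fisher p < 0.05. The required n per arm uses the plan's formula with the diluted placebo rate.

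| c | A1 difference (points) | A1 power, two-sided | A1 n needed | A2 difference (points) | A2 power, one-sided | A2 n needed |
|---|---|---|---|---|---|---|
| 0 | 18.0 | 94.8% | 88.3 | 11.0 | 79.0% | 140.6 |
| 10% | 16.2 | 90.1% | 106.1 | 9.9 | 71.6% | 168.9 |
| 20% | 14.4 | 82.7% | 130.6 | 8.8 | 63.0% | 207.8 |
| 30% | 12.6 | 72.3% | 165.6 | 7.7 | 53.4% | 263.4 |
| 50% | 9.0 | 44.7% | 303.9 | 5.5 | 33.6% | 484.2 |

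The A2 column uses a one-sided test because that is how 2.7 D sizes it. A two-sided Fisher test gives A2 68.2% power at c = 0. That drop comes from sidedness, which is a separate matter, and should not be attributed to non-study sugammadex.

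**The case against.** The strongest reply is that the intended background is clear. The neostigmine wording, the supply arrangement and the statement that 150 of 300 patients get the drug all describe a trial in which only the sugammadex arm receives it. Hypothesis A can also be read as a pragmatic question about adding sugammadex to whatever reversal is routine. In addition, the primary has room to spare: A1 keeps 82.7% power with one placebo patient in five affected.

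Much of this stands. The intent is visible, and the consequence for A1 is modest unless c is large. But the neostigmine text is rationale and section 2.8 is about supply; neither limits clinical stock. The pragmatic reading does not rescue the sample size, which has no allowance for dilution.

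Several stronger readings are tempting, and the documents do not support them.

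- **A reader might infer that rescue in the PACU makes the bias greatest on A2.** The calculation applies the same c to both endpoints and does not model rescue. Section 2.5 blinds care staff to the ventilation and train-of-four values, so they cannot treat on the readings that define A2. The reversal medication listed in Hypothesis F names no agent and could be opioid reversal.
- **A reader might expect use to drift upward during the trial.** No usage figure or trend is given, and 2.6 anticipates recruitment within 6 months.
- **A reader might see a contradiction with the dose statement in 2.3 D.** That statement describes what the study will administer, not total exposure, so no contradiction is shown.
- **A reader might ask for new data fields, or for PACU reversal to count as an A2 event.** Recording is already required. Rescoring would turn a measured ventilation endpoint into a composite to which 22% v 11% no longer applies.

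**Conclusion.** The gap is real. Nothing in the plan names the background reversal agent, excludes planned open-label sugammadex, or says how such patients are analysed. A clinician following 2.5 exactly can give a placebo patient the test drug.

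Under the model used, the direction is toward no effect. The size is conditional on c. A1 falls below 80% power somewhere between c = 20% and 30%. A2, which set the sample size and has no reserve, loses 7.4 points at c = 10% (79.0% to 71.6%) and 16.0 points at c = 20%.

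These figures assume that the planned event rates hold, that 33% and 22% come from patients not given sugammadex (the documents do not say), and that open-label drug has the full planned effect. A smaller effect would mean less dilution. The documents do not show that such use occurred or how likely it is. What is certain is what the text permits, not how much power is lost.

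**What to change.** 1. In 2.3 C.2, add an exclusion for patients whose treating clinician plans, before randomisation, to use non-study sugammadex for end-of-surgery reversal.
2. Reconcile the open wording on usual-care reversal in 2.5 A and 2.5 B.3 with the background implied in 2.3 D and 2.8.
3. In 2.7 B, state that all randomised patients stay in their assigned arm. From the medication data already collected, report non-study sugammadex by arm and site, separating use before and after the study dose.
4. Pre-specify a sensitivity analysis of A1 and A2. One workable form leaves out patients given non-study sugammadex before the study dose. Because the clinician is blinded, that use cannot depend on the assigned arm. Use after the dose can, so those patients should stay in.

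Clinicians remain free to treat as they judge. The cost is amendment wording and one extra table and analysis. The downside is that some screened patients are lost where open-label sugammadex is already routine, which could slow recruitment there.
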